**Cold symptom's duration (days) = Last symptomatic day – first symptomatic day + 1**

For a given symptom, a symptomatic day is a day the patient gave an answer other than negative to the corresponding question (“do not have this”). Missing answers will be imputed by the LOCF.

The considered symptomatic days are between D1 and either D15, or the end of the study, or the day before the recovery date, whichever occurs first. Symptomatic days from the recovery date will not be taken into account.

For each of the items 2 to 11 of the WURSS-21 questionnaire, the origin date will be the date of the first symptomatic day.

The considered event is the end of the symptom.

For patients who reported a negative answer to the corresponding question on the last day they answered to it, or for patients with a recovery date, the event date will be the last symptomatic day before his/her last day of completion of the questionnaire, or before the recovery date if it exists.

Patients who did not report a negative answer to the corresponding question on the last day they answered to it, and without recovery date, will be censored at D15 or at the end of the study, and the censoring date will be the date of D15 or the reference end date, whichever occurs first.

For patients who never reported the presence of a given symptom (never ticked “very mild”, “mild”, “moderate” or “severe”) and having completed the questionnaire at D1, the origin date for the symptom will be D1, the symptom will be censored at D1 and the corresponding duration will be zero. If patients who never reported the presence of a given symptom did not complete the questionnaire at D1, neither origin date nor censoring date will be defined for this symptom and the corresponding duration will be missing.

For each of the items 2 to 11 of the WURSS-21 questionnaire, duration endpoints will be summarized using the medians, with 95% confidence intervals (CIs) for the medians by group. Results for Healsea® Rescue\* group and Placebo group will be compared using Wilcoxon-Mann-Whitney test. Subjects will be analysed on the FAS.

For each duration, boxplots will be realized by treatment group. Numbers of available data and p-values will be printed on the figure.

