Objectives:	
Primary Objective:
 
 
- To compare the efficacy of Healsea® Rescue* and Placebo to improve the Quality of Life through symptoms of acute infectious rhinitis reduction in adults during a 7-day treatment period.
 
 
Secondary objectives:
 
 
- To compare the efficacy of Healsea® Rescue* and of the Placebo to reduce the duration of each infectious rhinitis symptoms rated by the WURSS 21
 
- To compare the efficacy of Healsea® Rescue* and of the Placebo to reduce the use of concomitant medication (antipyretics, systemic or local mucolytics, decongestants, antitussives, antibiotics)
 
- To compare the subject overall assessment on efficacy of Healsea® Rescue* and of the Placebo.
 
- Safety: to assess systemic and local tolerance of Healsea® Rescue* over the study period.
 

Endpoints:	
Primary Endpoint:  The primary endpoint is the AUC of Wisconsin Upper Respiratory Symptom Survey (WURSS-21) during first 8 days of symptoms.  The WURSS-21 will be assessed once daily during D1-D8.
 
Secondary Endpoints:
 
 
- AUC of the symptoms sub-score (items 2-11) and Quality of Life sub-score (items 12-20) of the WURSS-21 during first 8 days.
 
- Duration of cold symptoms in both groups assessed by means of the WURSS-21.  For each item, the duration is defined as the number of symptomatic days between D1 and the first day the subject reports not having the symptom for two consecutive days.  Notice that the duration may be censored at day 13-day 15.
 
- Frequency and number of days of use of concomitant treatments that may affect common cold symptoms (antipyretics, systemic or local mucolytics, decongestants, antitussives, antibiotics).
 
- Subject satisfaction regarding ease of use, efficacy, local tolerance and taste at the end of study visit (V2) using a 4-points categorical scale and of Global subject feedback on treatment use ("will you recommend the prescribed treatment for treatment of acute rhinitis?").
 
- Safety: Assessment of adverse events/incidents/foreseeable side effects throughout the study in both groups
 

Indication:	Treatment of acute rhinitis

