#### 7.1.4 Secondary Endpoints with methods and timing for assessing, recording and analysing variables

**--AUC of the symptoms sub-score (items 2-11) and Quality of Life sub-score (items 12-20) of the WURSS-21 during first 8 days**

**- Duration of cold symptoms** in both groups assessed by means of the WURSS-21.

For each item, the duration is defined as the number of symptomatic days between visit V1 and the first day the subject reports not to have this symptom for two consecutive days.

To be noticed that the duration may be censored at the end of study participation (visit V2). Should the patient have not ticked "not sick" for 2 consecutive days at the end of study visit, a WURSS-21 will be completed by the patient during the visit.

*Strictly Confidential*

- **Frequency and number of days of concomitant treatments use** that may affect common cold symptoms (antipyretics, systemic or local mucolytics, decongestants, antitussives, antibiotics).

By reducing duration of common cold symptoms, Healsea® Rescue\* will very likely reduce the use of common rescue medication. Concomitant treatments use will be reported in the e-diary by the patient throughout the study, validated by the investigator at the end of study visit before being reported in the e-CRF.

- **Subject satisfaction** regarding ease of use, efficacy, local tolerance and taste at end of study visit (V2) using a **4-points categorical scale** and of the **Global subject feedback** on treatment use ("will you recommend the prescribed treatment for treatment / prevention of acute rhinitis?").

Although subjective, these endpoints are pertinent because Healsea® Rescue\* is an OTC product which does not require physician prescription.

- **Safety:** Assessment of adverse events and incidents throughout the study in both groups. Adverse events/incidents will be reported in the e-diary by the patient, validated by the investigator at the end of study visit before being reported in the e-CRF.

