#### 10.2.2. Impact of the treatment on the cold symptoms' duration

Hereinafter, the “recovery date” is the first day of two last days the patient answered to the WURSS-21 questionnaire. The patient must have reported a negative answer to the question 1 (“not sick”) and the two last days must be consecutive. Otherwise, there is no “recovery date” for the patient.

For the items 2 to 11 of WURSS-21 questionnaire, the duration of the corresponding symptom is defined as the duration between first symptomatic day and last symptomatic day.

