## 12. CHANGES IN THE CONDUCT OF THE STUDY OR PLANNED ANALYSIS

The cold symptoms' duration was defined in the protocol as the number of symptomatic days between D1 and the first day the subject reports not having the symptom for two consecutive days.

Furthermore, since several patients still reported having symptoms while they reported they did not feel sick anymore at the question 1 during the two last days of completion of the WURSS-21 questionnaire, their positive answers to the cold symptoms' items have been considered as non-significant. Consequently, the question 1 has been taken into account instead of the corresponding items to determine the end of the cold symptoms' duration, however only on the condition that the two last days of completion were consecutive.

If the two last days of completion were not consecutive, positive answers to cold symptoms' items are still considered as symptomatic, even if the two last answers to the question 1 are negative. The symptom ends at the last symptomatic day if the patient reported the absence of this symptom after this day. Otherwise, the duration of the symptom is censored at D15 or at the end of the study, whichever occurs first.

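### SAP 10.2.2 measures each symptom's duration as a first-to-last span cut at the question 1 recovery date, not as the protocol's count of symptomatic days, and SAP 12 does not declare the span

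*SAP*

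**What the plan says.** **Protocol.** The Synopsis and section 7.1.4 give the same rule with D1 or V1 as origin: "the duration is defined as the number of symptomatic days between visit V1 and the first day the subject reports not to have this symptom" on two days running. The quantity is a number of symptomatic days, the stopping rule is applied to the item itself, and the duration may be censored at the end-of-study visit.

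**SAP 10.2.2.** For items 2 to 11 the formula is "Last symptomatic day – first symptomatic day + 1". Days are still classified item by item: "For a given symptom, a symptomatic day is a day the patient gave an answer other than negative to the corresponding question". A further date is then introduced from question 1 (how sick the patient feels): "the “recovery date” is the first day of two last days the patient answered to the WURSS-21 questionnaire". Those two days must be consecutive and both negative on question 1. The consequence is: "Symptomatic days from the recovery date will not be taken into account". A patient with a recovery date has an event for the symptom, even if the symptom was still being reported on those last days.

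**SAP 12.** The section on changes restates the protocol definition. It then explains, in the past tense, that several patients went on reporting symptoms after they no longer felt sick, and that these positive answers "have been considered as non-significant". It does not say that a count became a span, or that symptom-free days inside the span are counted.

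**The concern.** The SAP makes two separate changes.

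- **Count to span.** Symptom-free days between two reports now add to the duration. The item-level rule of two symptom-free days, which would have closed the episode, is gone. A single late report can therefore add several days.
- **Question 1 cut-off.** Positive symptom answers at the end of the diary are set aside, and what the protocol rule would leave censored can become a completed duration. SAP 12 shows that this rule was written with diary answers in view.

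Duration of each symptom is the first-listed secondary objective (Protocol 6.3), and Protocol 7.2.2 describes shortening symptom duration as the device's principal action. Ten between-group comparisons are planned, with p-values printed on the figures. A reader who knows the protocol definition would take these results for something they are not, and SAP 12 would not correct the mistake for the span.

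**Working it through.** The documents state no figure for the duration endpoint, so there is none to reproduce. The sample size in SAP 4 concerns the WURSS-21 AUC. The check applies both rules, as written, to hypothetical daily diaries for one item.

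**Inputs**
- Protocol rule (Synopsis, 7.1.4): find the first pair of consecutive days without the symptom, and count the symptomatic days before it. Taking the first or the second day of the pair as the end gives the same count.
- SAP rule (10.2.2): if the last two answered days are consecutive and both not sick on question 1, the first of them is the recovery date. Drop symptom answers from that date, then compute last symptomatic day − first symptomatic day + 1.

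**Results** (1 = symptom present, 0 = absent, from D1)

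| Diary for one item | Not sick on question 1 | Protocol | SAP |
|---|---|---|---|
| 1111000 (no gap) | D6, D7 | 4 | 4 − 1 + 1 = 4 |
| 1101100 (one-day gap) | D6, D7 | D1, D2, D4, D5 = 4 | 5 − 1 + 1 = 5 |
| 110000100 (return after four free days) | D8, D9 | D1, D2 = 2 | 7 − 1 + 1 = 7 |
| 1000000100 (D1 and D8 only) | D9, D10 | D1 = 1 | 8 − 1 + 1 = 8 |
| 1100000000 (ends early, patient still sick) | D9, D10 | 2 | 2 − 1 + 1 = 2 |
| 1111111 (still present when not sick) | D6, D7 | rule not met; 7 days recorded, censored at V2 | 5 − 1 + 1 = 5, event |
| 0001100 (onset on D4) | D6, D7 | 0 as worded | 5 − 4 + 1 = 2 |

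**Reading the table**
1. Without gaps the rules agree. A one-day gap adds 5 − 4 = 1 day. The two late returns add 7 − 2 = 5 and 8 − 1 = 7 days.
2. The late-return results have conditions. The patient must not have given two consecutive not-sick answers earlier, because the diary would then have stopped (SAP 13.3). There must also be a negative last answer to the item or a later recovery date; otherwise SAP 10.2.2 censors the symptom.
3. If the protocol wording were read loosely as elapsed time, the one-day gap would give 5 under both rules. The late returns would still give 2 against 7 and 1 against 8, because the protocol episode closes at the first two free days.
4. The recovery date is the second-to-last answered day, so the cut-off removes at most two days of answers. In the sixth row it removes D6 and D7 and replaces censoring by an event at 5 days.
5. The fifth row shows that an item's own end is kept: question 1 stayed positive to D8, yet the SAP duration is 2.
6. The last row shows a defect in the protocol wording. Starting the search at the item's first symptomatic day (D4) gives D4 and D5, so 2 days, with no need for a span.

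**The case against.** The other side has real points.

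- **Inferential weight.** SAP 6.3.1 makes only the primary criterion conclusive. Duration results are descriptive, with p-values for information. This stands and limits the importance of the point.
- **The protocol rule is not a clean standard.** As worded it gives 0 days for a late-onset symptom. The diary also stops on two not-sick answers to question 1, not on two symptom-free days per item, so for a patient with a residual symptom the rule cannot be met. This stands. It is why the protocol rule should not simply be restored as the only analysis.
- **A return within one cold may fairly be counted as continued illness.** This is defensible, but it is a different quantity and should be declared as such.
- **SAP 12 does disclose.** It declares the use of question 1. It also declares an end at the last symptomatic day for patients whose final two entries are not consecutive. The span and its gap days remain undeclared.

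Four stronger readings are tempting, and the documents do not support them. A reader might infer that a symptom's own duration is no longer measured, or that all ten durations end on one common date. In fact each item keeps its own first and last day, and question 1 only trims the end. A reader might infer that the span was chosen after seeing data, but SAP 12 gives that reason for the question 1 rule only. A reader might infer that treatment codes were known. Protocol 9.3 plans a blind review before lock, which also validates the SAP, and Protocol 7.1.2 places unblinding after lock. Finally, a reader might infer that the change favours the device. Gap days lengthen durations and the cut-off shortens them, and nothing shows how either falls by arm.

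**Conclusion.** The point holds as a departure from the protocol definition that is only partly declared. Per patient and symptom, the difference in the worked diaries runs from 0 days (no gap) to 7 days (present on D1 and D8 only), and the cut-off can convert censoring into an event. These are illustrations. The documents do not say how often gaps, late returns or residual symptoms occur, so neither the average shift nor the effect on the comparison between arms can be estimated.

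The data-driven origin is documented for the question 1 cut-off. For the span it is unknown, and unblinded choice is not shown for either. The primary AUC conclusion is not touched. The conclusion assumes daily diary entries and the protocol rule read as a count up to the first pair of symptom-free days.

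**What to change.** 1. For each of items 2 to 11, also derive the protocol-defined duration: symptomatic days from the item's first symptomatic day to the first of two consecutive days without that symptom. Starting at the first symptomatic day removes the late-onset defect.
2. Flag as censored any patient whose diary ends before that condition is met, and compare the arms by a method that handles censoring, for example Kaplan-Meier medians with a log-rank test. Show the number censored by arm, because a diary that stops when the patient feels well does not censor independently of the symptom.
3. Present this beside the SAP 10.2.2 version, and draw a conclusion on duration only where both agree.
4. In SAP 12, list the change from count to span and the counting of gap days. Give the date and blinding status of both this change and the question 1 cut-off. Protocol 8.10 already asks for deviations from the planned analysis to be reported.

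The cost is one more derived variable and table per symptom, from diary data already collected. The two versions may disagree, and the report would then have to say so.

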#### *7.3.1.4 Subject lost to follow-up*

If a patient cannot be contacted to collect follow-up information even beyond the 7 days from visit 2, he/she will be considered "lost to follow-up". But before declaring that a patient is "lost to follow-up", the Principal Investigator (or his/her team) must do his/her best effort to contact patients and attempts should be made via all available routes. A certified letter should be sent to the permanent address on file.

The methods used to attempt contacting the patient should be noted in the patient medical file.

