**Visit 2 (V2) – (Day 13-15): end of study**

The investigator or his/her delegated designee will:

- Perform a physical and clinical examination. A pharyngeal nasal swab will be performed by the investigator or by the delegated study nurse to check for absence or presence of SARS-CoV2.
- Validate adverse events pertinent in the context of the common cold and of additional study procedures /incidents linked to medical device use and concomitant medications reported in the e-diary and complete the e-CRF accordingly and report any new relevant safety events.
- Ask the patient to complete the WURSS-21 if he/she still has symptoms.
- Assessed the compliance to the treatment by weighting the device returned by the subject. In case of nasal spray dysfunction and attribution of a new treatment using the back-up randomization list, the compliance will be assessed by weighting both devices. If a nasal spray is lost, the investigator will ask the patient to specify the number of missed nasal spray use and will report the data into the e-CRF.
- Ask the patient to complete a satisfaction questionnaire.

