### 6.3. Statistical/Analytical issues

#### 6.3.1. Significance level

All statistical analyses will be performed at the 0.05 global significance level (type I error rate), using one-sided tests.

The statistical results are conclusive for the primary efficacy criterion.

All the other statistical results have to be considered within a descriptive perspective and not as inferential issues. No adjustment for Type I error is done. P-values of statistical tests will be provided for information only.

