**6.4. General conventions and calculated variables****6.4.1. Subject reference start/end dates**

For each subject, the reference dates will be the following:

- The reference start date is the date of inclusion visit.
- The reference end date is the date when subject was determined to have ended the trial.

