## 7. STUDY PATIENTS

### 7.1. Disposition of patients

Screened subjects (signed informed consent) and included subjects will be summarised using frequencies and percentages as well as reasons of non-selection/non-inclusion, if applicable. The number and percentage of subjects who withdrew prematurely after inclusion, are lost to follow-up as well as the number of completers will be described by treatment group and overall. All withdrawn subjects after their inclusion will be described regarding their main reason for withdrawal.

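### Symptom durations are given censoring dates but are then compared by a plain rank test as if every duration had been observed

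*SAP*

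**What the plan says.** SAP 10.2.2 treats the duration of each of WURSS-21 items 2 to 11 as time to an event. The origin is the first symptomatic day and the event is the end of the symptom. For a patient whose last answer is still positive and who has no recovery date, "the censoring date will be the date of D15 or the reference end date, whichever occurs first". SAP 6.4.1 defines that end date: "The reference end date is the date when subject was determined to have ended the trial". For a patient who never has the symptom but completed D1, "the symptom will be censored at D1 and the corresponding duration will be zero".

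The displayed formula, however, runs from the first to the last symptomatic day and has no term for censoring. The analysis is a median with 95% CI per arm, boxplots, and a comparison in which the Healsea Rescue "group and Placebo group will be compared using Wilcoxon-Mann-Whitney test". Protocol 8.4 names the same test. SAP section 12 revises the definition of duration and repeats the censoring rule, but leaves the test alone. The mock duration table in SAP 13.2 lists N, missing, mean, median, quartiles, range and a Wilcoxon p-value. It has no row for events or censored patients.

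SAP 6.3.1 sets the status of every non-primary test: "P-values of statistical tests will be provided for information only".

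**The concern.** A Wilcoxon-Mann-Whitney test has no place for a censoring indicator. A patient known only to have been symptomatic for at least 4 days enters the ranks at a single number, and so do the median and the boxplot. The definition produces censoring information that nothing downstream uses.

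Symptom duration is the first secondary objective and covers ten symptoms. If the value given to unresolved durations is arbitrary, and drop-out differs between arms in amount or type, the medians and p-values partly reflect how patients left. A reader of the report could not see this, because no count of censored durations per symptom is planned.

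**Working it through.** **Plan figures.** The documents give no power or effect size for duration. The only usable input is drop-out of about 10% (SAP 4), and its arithmetic reproduces: 180 / 0.9 = 200. That is about 10 patients per arm, with no split by arm or type of exit.

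**What a censored patient is worth.** Take a patient symptomatic from D1 whose last diary answer, on D4, is positive.

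- Censoring date ends the duration, reference end date D4 (withdrawal): 4 − 1 + 1 = 4 days.
- Censoring date ends the duration, end date recorded after D15: 15 − 1 + 1 = 15 days. This could happen to a lost patient, since Protocol 7.3.1.4 reads: "If a patient cannot be contacted to collect follow-up information even beyond the 7 days from visit 2".
- Only answered days count (displayed formula): 4 days, whatever the exit.
- LOCF in 10.2.2 fills wholly blank days: up to 15 days again. SAP 6.4.6 bars imputing scores on such days; 10.2.2 does not say whether its own LOCF does the same.

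In every case the data say only that the symptom lasted at least 4 days. Likewise, a symptom that starts on D5 and persists on D15 is entered as 15 − 5 + 1 = 11 days and ranks below an observed 12.

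**Stopping the diary but attending V2.** Protocol 7.4.1 tells the site: "Ask the patient to complete the WURSS-21 if he/she still has symptoms". A patient last positive on D4 and well at V2 then has no V2 form and stays censored. Protocol 7.1.4 and the flow chart instead require a form unless two consecutive not-sick days were recorded. A negative answer on D15 then dates the end of the symptom to D4 (4 days, if blank days are not filled), although the last symptomatic day could be anywhere from D4 to D14, a duration of 4 to 14 days.

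**Size.** Simulation, with inputs that are assumptions and not in the documents: 100 per arm, one-sided 0.05, no true effect. Durations are Weibull (shape 1.5 or 2.5; median 7 days, or 75% over by day 7). Drop-out falls on D2–D5 or D2–D12, unrelated to recovery, and completers are censored on D13–D15. There are 4000 runs per cell. Withdrawn patients are valued at the exit day and lost patients at D15. Ranges run over the eight combinations.

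| Drop-out, device / placebo | Exit | Planned test | Gehan-Wilcoxon, last answered day |
|---|---|---|---|
| none | – | 4.6–5.3% | 4.6–5.3% |
| 10% / 10% | all withdrawn | 4.4–5.4% | 4.7–5.4% |
| 10% / 10% | all lost | 4.1–5.3% | 3.9–5.6% |
| 10% / 10% | 25% lost (device), 75% lost (placebo) | 8.0–25.3% | 4.1–5.4% |
| 12% / 8% | all withdrawn | 6.0–11.4% | 4.5–5.4% |
| 15% / 5% | all withdrawn | 7.7–26.2% | 3.6–4.8% |
| 15% / 5% | half lost | 4.3–5.2% | 4.0–4.8% |
| 15% / 5% | all lost | 0.5–2.8% | 3.4–4.6% |

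The all-withdrawn rows also describe the answered-days reading, because every drop-out then takes the value of the last diary day. Rows with lost patients apply only if the censoring date ends the duration and the end date is recorded late. Equal drop-out of the same type is harmless under the null because both arms then share one distribution, however badly the values are set.

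Other results under the same inputs:

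- Median at 10% drop-out, planned minus true: −0.72 to −0.12 day if all withdraw, −0.11 to −0.02 if half are lost, +0.07 to +0.56 if all are lost. Kaplan-Meier at the last answered day: +0.02 to +0.08.
- Power for a 15% shorter duration at 10% / 10%: 0.7 to 8.9 points below Gehan-Wilcoxon.
- Changing the test but keeping the D15 date does not help: at 15% / 5%, all lost, Gehan-Wilcoxon rejects in 0.5–2.8% and log-rank in 0–1.5%.

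**Where the replacement fails.** If drop-outs stop answering because the symptom has ended (median 7 days, shape 1.5 or 2.5, 2000 runs), a rank test on the last positive day rejects in 4.8% at 15% / 5% and 3.9–5.1% at 5% / 15%. Gehan-Wilcoxon, which censors those patients, rejects in 1.0–1.2% and 15.6–17.2%.

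**The case against.** The strongest reply is that little hangs on this. The tests are declared informational, with no multiplicity claim. The one documented drop-out figure has no imbalance, and with balance the planned test holds its level. Two features should limit early drop-out: SAP 7.2 refers to daily calls when the WURSS-21 is not completed between D1 and D8, and Protocol 7.3.9 ties payment to completion. Disposition is also visible, since the SAP says that patients who "are lost to follow-up as well as the number of completers will be described by treatment group and overall". All of this stands, and it keeps the point away from the primary conclusion. It does not supply the missing rule for unresolved durations or the missing counts per symptom, and the reported medians shift even with balanced drop-out.

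A reader might go further and infer that the plan definitely ranks withdrawals short and losses long. The documents do not support that. The split needs the censoring date to end the duration, which the text of 10.2.2 and section 12 suggests but the displayed formula does not. It also needs a late end date for lost patients. Protocol 7.3.1.4 says when a patient is considered lost, not which date is recorded, and SAP 6.4.3 lets the Validation Committee extrapolate missing end dates.

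A reader might also infer that a censoring-aware test settles the matter. It does so only if drop-out is unrelated to recovery.

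Finally, the Wilcoxon entry in the mock table could be read as the Gehan version. The name given in the text, the boxplots and the absence of a censored count all point to the ordinary rank-sum test.

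**Conclusion.** The point holds as a flaw in a secondary, descriptive analysis that should be corrected. Censored durations are analysed as observed, and the value given to an unresolved symptom depends on a rule the SAP leaves open. Patients who stop the diary and then attend V2 can be mis-valued too.

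At about 10% drop-out, equal in amount and type, null rejection stays near 5%, the median shifts by at most about 0.7 day, and some power is lost. With no early drop-out, censoring at D13–D15 does no visible harm. Error rates move only with an arm imbalance, and the direction depends on the type of exit and the reading of the rule. The 8–26% at 15% versus 5% illustrates what an assumed imbalance would do; it does not forecast this trial.

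The zero for never-symptomatic patients is a usable all-patient outcome, but a value used as zero in the ranks is not a censored one, so the label and the use conflict.

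**What to change.** 1. State one rule: an unresolved symptom is censored at the last day the item was answered, not at D15 or an administrative end date. Say whether LOCF applies to wholly blank days.
2. Report Kaplan-Meier medians with 95% CI per arm and a Gehan-Wilcoxon test, which stays closest to the plan; log-rank is an alternative.
3. Add events, censored and never-symptomatic patients, per arm and symptom, to the mock duration table.
4. Report never-symptomatic patients separately, or keep them at duration zero in an all-patient comparison, without calling them censored at D1.
5. State that the main analysis assumes drop-out unrelated to recovery. Add a sensitivity analysis that treats drop-outs as recovered at their last positive day and, where a gap precedes a negative V2 answer, uses the interval between the last positive and the first negative answer.

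The cost is SAP wording, a few table rows, a standard survival procedure and one sensitivity analysis. The e-diary already holds the last answered day. What remains is a censoring assumption that the data cannot test.
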